### 5.1.2 Visit Window

In order to summarize longitudinal data per timepoint, assessments will be allocated to visits using pre-defined time windows. Unless otherwise specified, the Schedule of Activities and windowing in the protocol will be used. The deviations from visit windows specified in the protocol will be documented by site monitor in Monitor Express portal.

## 5.2 Study Populations

For the purposes of the analyses, the following populations are defined:

**Table 3 Study Populations for Analyses**

Population	Description
Enrolled	All participants who sign the ICF.
Full analysis set (FAS)	All enrolled participants or all randomized patients (for the randomized phase of the study). This population will be used for baseline and disposition summaries as well as for the analysis of secondary endpoints related to efficacy.
Safety population	All enrolled (or randomized for the randomized phase of the study) participants who received any quantity of study intervention, regardless of their eligibility for the study. The safety evaluation will be performed based on the study treatment actually received.  The safety population will be used for all baseline, exposure, physical function, cognitive function, daily function, and safety analyses. For the evaluation of each endpoint using an instrument or questionnaire, participants with baseline and at least one post-baseline assessment will be included.

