5.4 Screen Failures

Screen failures are defined as participants who consent to participate in the clinical study but are not subsequently entered in the study. A minimal set of screen failure information is required to ensure transparent reporting of screen failure participants to meet the Consolidated Standards of Reporting Trials (CONSORT) publishing requirements and to respond to queries from regulatory authorities. Minimal information includes demography, screen failure details, eligibility criteria, and any serious adverse event (SAE).

During the screening period, if a participant has failed a test, the test may be repeated if the investigator has determined that the repeated screening test does not expose the participant to an unjustifiable health risk. The participant may be eligible for study participation if the repeated test meets the screening criteria and protocol window.

Individuals who do not meet the criteria for participation in this study (screen failure) may be rescreened. A participant who is rescreened is required to sign another ICF.

6. Study Intervention

Study intervention is defined as any investigational intervention(s), marketed product(s), placebo, or medical device(s) intended to be administered to a study participant according to the study protocol.

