9.3 Populations for Analyses

For the purposes of the analysis, the following populations are defined:

Population	Description
Enrolled	All participants who sign the ICF
Full analysis set (FAS)	All enrolled participants or all randomized patients (for the randomized portion of the study). This population will be used for baseline and disposition summaries as well as for the analysis of secondary endpoints related to efficacy.
Safety population	All enrolled (or randomized for the randomized portion of the study) participants who received any quantity of study intervention, regardless of their eligibility for the study. The safety evaluation will be performed based on the intervention actually received. The safety population will be used for all baseline, exposure, physical function, cognitive function, daily function, and safety analyses. For the evaluation of each endpoint using an instrument or questionnaire, participants with baseline and at least one post-baseline assessment will be included.

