## 5.0 Statistical Methods

### 5.1 General

Demographic and baseline characteristics, efficacy assessments, and safety data will be summarized for the lead-in Phase and for the Randomization Phase separately. The Lead-in Phase summary will be based on a single group of subjects treated with darolutamide, while the Randomization Phase will be summarized by darolutamide, enzalutamide and overall groups. Unless otherwise stated, all analyses described below will be applied to both phases of the trial.

All variables will be analyzed with appropriate statistical methods. Continuous data will be presented as n, mean, standard deviation, median, quartiles, minimum, and maximum. Continuous variables will be described by absolute value and as change from baseline per analysis time point. Categorical data will be presented as frequency counts, percentages and 95% CI. All raw data collected will be listed.

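### Does the lead-in full analysis set wrongly take in screen failures who were never treated?

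*SAP*

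**What the plan says.** SAP 5.2, Table 3, defines three populations. Enrolled is "All participants who sign the ICF". The FAS is "All enrolled participants or all randomized patients (for the randomized phase of the study", and its use is stated as: "This population will be used for baseline and disposition summaries as well as for the analysis of secondary endpoints related to efficacy". The Safety population is limited to those who took some study drug, and its row adds: "The safety population will be used for all baseline, exposure, physical function, cognitive function, daily function, and safety analyses". Protocol 9.3 has the same FAS definition: "All enrolled participants or all randomized patients (for the randomized portion of the study".

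Protocol 5.4 says: "Screen failures are defined as participants who consent to participate in the clinical study but are not subsequently entered in the study". It also lists what is recorded for them: "Minimal information includes demography, screen failure details, eligibility criteria, and any serious adverse event (SAE".

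SAP 5.1 sets the scope of the summaries: "Demographic and baseline characteristics, efficacy assessments, and safety data will be summarized for the lead-in Phase and for the Randomization Phase separately". It goes on to base the lead-in summary on one group, those treated with darolutamide.

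**The concern.** The definitions chain together badly. A man who signs consent is Enrolled, every Enrolled man is in the lead-in FAS, and screen failures have signed consent. The FAS row has no dosing condition, although the Safety row does. The lead-in has one arm, so no randomization list narrows the set.

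Demography is recorded for screen failures and is part of the baseline table in SAP 5.3.6. Under the literal FAS, that table could describe men who never entered the study. The disposition table in SAP 5.3.2 is exposed as well, since Table 3 assigns it to the FAS and it reports reasons for stopping treatment as percentages. SAP 5.4.2 gives no denominator for PSA response, so that percentage could be diluted.

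A smaller point concerns both phases: Table 3 gives baseline summaries to both the FAS and the Safety population and does not say which table is the main one.

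**Working it through.** **Which men the plan means**

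- Table 3 and Protocol 9.3, read literally: all who consented.
- SAP 5.1: those treated with darolutamide, for baseline, efficacy and safety summaries alike.
- Table 3, Safety row: dosed participants, for baseline among other analyses.
- SAP 3.4: about 30 participants receive study drug. Exact binomial limits with n = 30 reproduce all six rows of SAP Table 2. For 6/30, the lower limit is the 0.025 quantile of Beta(6, 25) = 7.71% and the upper limit is the 0.975 quantile of Beta(7, 24) = 38.57%, as printed. The plan's own lead-in denominator is therefore the treated group.
- Protocol 6.1.1 expects every enrolled participant to do accelerometry, and Protocol 10.1.3 places consent before enrollment. Neither fits a definition in which signing the form is enrollment.

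Only the literal wording brings in screen failures.

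**Size if it were read literally**

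Let s be the screen-failure share, which the documents do not give. With 30 treated, N = 30/(1 − s).

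| Assumed s | N (unrounded) | N | Never treated | 30/N |
|---|---|---|---|---|
| 0% | 30.0 | 30 | 0 | 1.00 |
| 10% | 33.3 | 33 | 3 | 0.91 |
| 20% | 37.5 | 38 | 8 | 0.79 |
| 30% | 42.9 | 43 | 13 | 0.70 |

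The last column is the factor by which a disposition percentage would shrink.

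**PSA response.** Assume 15 responders among 30 treated, 50.0%. Counting never-treated men as non-responders would give 15/33 = 45.5%, 15/38 = 39.5% or 15/43 = 34.9%. SAP 5.1.1 argues against this: baseline is the last value before first exposure and is otherwise missing. A never-treated man has no baseline, so no reduction can be computed for him. Treated as missing, he drops out and the rate stays at 50.0%.

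**Time to PSA progression.** In the lead-in, SAP 5.4.2 starts the clock at first dose, so a never-treated man has no time origin. Even if entered as censored at time zero, he leaves the risk set before the first event, and each Kaplan-Meier factor (1 − events/at risk) is unchanged. A simulated check with 30 treated and 8 such men gave an identical curve and median. Overall survival is not analyzed in the lead-in.

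**Results that guide decisions.** Protocol 4.1 names TUG, the Short Physical Performance Battery and cognitive tests for the lead-in evaluation. SAP 5.5 puts these on the Safety population. Protocol 9.1 plans no formal test in the lead-in. The randomized-phase FAS is everyone randomized, so the planned 120 participants and the 85% power are untouched.

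**Baseline assigned twice.** In the randomized phase the two sets differ only by men randomized and never dosed. At assumed shares of 0, 2 and 5% of 120, that is 0, 2.4 and 6.0, or about 0, 2 and 6 men.

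**The case for a change.** The best case for a change is that Table 3 is the formal definition, the SAP is where populations should be settled, and one sentence would cure the inconsistency at no cost in data. SAP 5.1 can also be read as describing table columns, one group against several, and not as defining a population. On that reading, nothing in the SAP formally overrides the literal FAS.

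Part of this stands. The wording is inconsistent, and the disposition table is exposed along with the baseline table. The rest is weaker. Even if SAP 5.1 only describes columns, its column is headed by men treated with darolutamide, and a screen failure does not belong there. The Safety row independently assigns baseline to dosed participants, so the baseline table could, but need not, include screen failures. Reasons for stopping treatment do not apply to men who never started, and SAP 5.3.1 already gives enrollment and eligibility their own summary. Limiting the lead-in FAS to dosed men would simply make it the Safety population under a second name. Showing baseline for both sets is ordinary practice and is not an error.

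**Conclusion.** This is a clerical looseness in the word Enrolled, and no change to the plan is needed. Analysts reading Table 3 together with SAP 5.1 and 5.1.1 would summarize the roughly 30 treated men and report screen failures with enrollment. If they did not, the slip would be visible: the lead-in baseline or disposition N would exceed the Safety N, by about 3 to 13 men at assumed screen-failure shares of 10 to 30%.

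Those counts rest on assumed shares and on 30 treated. The unchanged PSA response rate rests on treating never-treated men as missing, which SAP 5.1.1 implies but SAP 5.4.2 does not state. The Kaplan-Meier estimates, the function endpoints, the randomized-phase power and the planned tests do not depend on this wording. Rewriting the definition would tidy a displayed N and some descriptive percentages in a single-arm phase, without altering what the trial does or concludes.

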9.1 Statistical Hypotheses

There is no formal statistical hypothesis testing for the lead-in part of the study.

For the randomized portion of the study, this study will test the null hypothesis of no difference in the proportion of participants with a worsening in physical function as assessed by the TUG test in the two arms against the alternative hypothesis that there is a difference.

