9.4.2 Safety Analyses

All safety analyses will be performed on the Safety population.

Endpoints measuring physical function, cognitive function, and daily activity will also be performed on the Safety population.

Endpoint	Statistical Analysis Methods
Primary	
The primary variable in this study is the proportion of participants with a worsening in TUG time during the 24-week period from baseline. Worsening is defined as an increase of at least 1 second in TUG time from baseline by 24 weeks.
 
 At each assessment, change in TUG test time (seconds) from baseline will be calculated, and the status will be categorized as: improved, stable, or declined using the MCID of 1 second. Decline in physical function is defined as at least a 1-second increase from baseline in TUG time in each arm by 24 weeks. The proportion of participants with a decline and the 95% CIs will be summarized for each treatment arm. This rate will be compared between the two arms using Cochran-Mantel-Haenszel test adjusting for stratification factors as captured by IWRS.

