#### 4.2 Missing Data

The primary endpoint is the Proportion of patients with worsening in TUG time from Baseline. Primary endpoint-related missing data will not be imputed, but a sensitivity analysis will be conducted by replacing missing TUG times with  $\geq 1$  second increase.

All missing or partial date will be presented in the patient listings, as they are recorded on the case report form, unless otherwise specified.

A conservative approach will be taken for partial or missing dates of AE and concomitant medications. Partial dates with missing day only will be imputed to either first of month, or first dose date if it falls in the same month. Partial dates with missing month will be imputed to either

January 1 or first dose date if it falls in the same year. Completely missing dates will be imputed using first dose date, unless the end date suggests it could have started prior to this in which case the imputed date will use 1st January of the same year as the end date. In all cases, imputed start dates must be compatible with reported end dates.

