#### **5.4.1 Primary Efficacy Endpoint Analysis**

There is no primary efficacy endpoint in this study.

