## 5.5 Safety and Tolerability Analysis

Safety analyses are based on the Safety population. Descriptive statistics are used to summarize the safety parameters. Safety data including AEs, AESI, laboratory parameters, vital signs, exposure and KPS. The protocol schedule of events and windowing will be used for the applicable safety table assessments.

Endpoints measuring physical function, daily activity and cognitive function will also be performed on the Safety population.

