### 5.5.1 Primary Endpoint Analyses

The primary variable in this study is the proportion of participants with a worsening in TUG time during the 24-week period from baseline, using the best TUG time out of the measured assessments during study visits (two or

three assessments). Worsening is defined as an increase of at least 1 second in TUG time from baseline.

The proportion of participants with a worsening in TUG time and the (exact) 95% CIs will be summarized by treatment arm. A comparison between treatment arms will be made using Cochran-Mantel-Haenszel (CMH) test adjusting for Age (<75, ≥75). A sensitivity analysis will be provided by replacing missing TUG times with ≥ 1 second increase. Primary endpoint (worsening in TUG) analysis will be performed by age (<75, ≥75), metastatic state (nmCRPC, mCRPC), Pain (yes, no pain), and opioid use (yes, no opioid use). Information on pain and opioid use will be retrieved from an examination of medical history and prior medication CRFs.

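### The randomised TUG comparison is planned on dosed participants with a post-baseline TUG; no all-randomised analysis is stated, and the sensitivity analysis may not cover those left out

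*SAP*

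**What the plan says.** - **Hypothesis.** For the randomised phase, Protocol 9.1 says "this study will test the null hypothesis of no difference in the proportion of participants with a worsening in physical function", with TUG as the measure. SAP 5.5.1 tests this with a Cochran-Mantel-Haenszel (CMH) comparison of treatment arms, adjusted for age.
- **Where TUG sits.** SAP 5.4.1 says "There is no primary efficacy endpoint in this study", and TUG is handled under safety. Protocol 9.4.2: "Endpoints measuring physical function, cognitive function, and daily activity will also be performed on the Safety population". SAP 5.5: "Endpoints measuring physical function, daily activity and cognitive function will also be performed on the Safety population".
- **Who is in that set.** Protocol 9.3 defines it as "All enrolled (or randomized for the randomized portion of the study) participants who received any quantity of study intervention". Protocol 9.3 and SAP Table 3 both add a data condition: "For the evaluation of each endpoint using an instrument or questionnaire, participants with baseline and at least one post-baseline assessment will be included". The full analysis set (FAS) contains all randomised participants, but is assigned only to baseline, disposition and secondary efficacy summaries.
- **Missing data.** SAP 4.2: "Primary endpoint-related missing data will not be imputed". SAP 5.5.1: "A sensitivity analysis will be provided by replacing missing TUG times" by a worsening of at least 1 second. Neither section says in its own text which participants this covers.
- **Schedule.** In SAP Table 8-2 the first post-baseline TUG is at Week 12 and the next at Week 24. None is scheduled at the end-of-treatment visit. SAP 5.1.1 defines baseline relative to first exposure to study drug.

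**The concern.** A test of a randomised difference is protected by randomisation only if those randomised are compared as randomised. Under the plan two groups leave the TUG comparison: participants who never start drug, and participants who start but have no TUG from Week 12 on. If leaving is related to physical decline, or its extent differs between arms, the observed difference can shrink or grow and the one-sided 10% error can move.

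The planned sensitivity analysis should be the check on this. Because it sits under SAP 5.5, undosed participants are outside it by default. If the post-baseline condition applies as well, participants with no post-baseline TUG are also outside it, and they are the ones it would mainly need to cover. The lead-in phase has no hypothesis test and is not affected.

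**Working it through.** **1. The plan's own power.** Inputs from SAP 3.4: 120 participants, 1:1, 20% vs 40%, one-sided alpha 10% (z = 1.2816), 10% drop-out. Evaluable per arm: 60 × 0.9 = 54.
- Unpooled: SE = √[(0.2×0.8 + 0.4×0.6)/54] = √(0.40/54) = 0.0861. Power = Φ(0.20/0.0861 − 1.2816) = 85.1%.
- Pooled variance under the null: 84.4%.
- With 60 per arm: 87.9% unpooled, 87.2% pooled.

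The stated 85% is reproduced at 54 per arm. The sample size therefore already treats about 12 participants as absent, and non-informative loss of that order is budgeted.

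**2. Informative loss and the error rate.** Assumptions, not from the documents: no true difference, 30% worsening in both arms, 5% of one arm lost (3 of 60), share w of those lost being worseners. The observed rate in that arm is (0.30 − 0.05w)/0.95 with n = 57; the other arm stays at 30% with n = 60. The one-sided 10% error in favour of the arm that lost participants is Φ(difference/SE − 1.2816).

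| w | Observed rate | Spurious difference | One-sided error |
|---|---|---|---|
| 0.3 (non-informative) | 30.0% | 0 | 10.0% |
| 0.5 | 28.9% | 1.1 points | 12.4% |
| 0.6 | 28.4% | 1.6 points | 13.7% |
| 1.0 (extreme) | 26.3% | 3.7 points | 20.1% |

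Exact binomial enumeration of the pooled z test gives 12.4%, 13.8% and 20.2% for the last three rows. If the loss is in darolutamide, this is false evidence for darolutamide; if it is in enzalutamide, the shift runs the other way.

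**3. What the sensitivity analysis can see.** Assume 12 dosed participants lack any post-baseline TUG, 10 on darolutamide and 2 on enzalutamide, and about 20% and 40% of the rest worsen.
- Post-baseline condition applied: nobody without a post-baseline TUG is left to impute. The counts stay 10/50 vs 23/58, z = 2.21, one-sided p = 0.014.
- Condition not applied: 20/60 vs 25/60, z = 0.94, one-sided p = 0.173.

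The unstated choice can decide whether the result is inside or outside the 10% level.

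**4. Counting missing as worsened is not always conservative.** Assume no true difference (30% in both arms) and 5% non-informative loss in enzalutamide only.
- The enzalutamide rate becomes 0.30×0.95 + 0.05 = 33.5%, against 30%, with 60 per arm.
- The one-sided error in favour of darolutamide is Φ(0.035/0.0849 − 1.2816) = 19.2%, or 19.6% by exact enumeration. The restricted set stays near 10%.

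**5. Power under this rule.** With 10% missing in both arms the rates are 0.2×0.9 + 0.1 = 28% and 0.4×0.9 + 0.1 = 46%. Power with 60 per arm is 78.7% unpooled, 78.1% pooled.

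All figures use an unstratified two-proportion approximation to the planned age-adjusted CMH test.

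**The case against.** The strongest reply is that TUG is deliberately classed as a safety endpoint, that few participants will be lost, and that the randomised phase will be re-specified anyway. Much of this stands.

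- Protocol 7.1 keeps participants who stop drug in the study for 52 weeks, and a Week 24 TUG alone meets the data condition, so the group with no post-baseline TUG should be small.
- Classing TUG as safety explains the choice of set. It does not settle the choice for a tested randomised comparison.
- The randomised phase is conditional, and SAP 3.1 says its endpoint, time frame and sample size will be reconsidered. However, SAP 5.1 applies the analyses to both phases unless otherwise stated, and SAP 5.5.1 already specifies the between-arm test.

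Some stronger readings are tempting but not supported:

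- **That TUG is grouped by drug received.** The actual-treatment wording in SAP Table 3 and Protocol 9.3 is written for the safety evaluation. SAP 5.5.1 compares treatment arms, and Protocol 9.4.2 adjusts for the strata recorded at randomisation.
- **That the sensitivity analysis has no analysis set at all.** It falls under the SAP 5.5 default; only the post-baseline condition is open.
- **That no loss rate is given.** SAP 3.4 assumes 10% drop-out. What is absent is the rate by arm and by reason.
- **That non-start will differ by arm.** Only enzalutamide is obtained by pharmacy prescription, and dosing may begin up to 21 days after randomisation. But first administration is at the study centre in both arms, and entry requires eligibility for enzalutamide. A difference is possible, not shown.

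**Conclusion.** The concern holds as a gap in the analysis set, and should be fixed before the randomised phase begins. Followed as written, the plan removes some randomised participants from its one stated hypothesis test and offers no TUG analysis that restores them all. The sensitivity analysis leaves out the undosed and may leave out everyone with no post-baseline TUG.

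A reader might infer that the primary result will be biased or that the sample size is wrong. Neither follows. The 85% power reproduces, and loss unrelated to outcome leaves the expected difference unchanged. The exposure is to informative or unequal loss. Its size is assumption: a one-sided error of 12.4% to 20.1% for 5% loss in one arm, where the upper end requires every lost participant to be a worsener.

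**What to change.** When the randomised phase is re-specified after the lead-in:

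1. Define the TUG CMH comparison on the FAS by assigned arm, adjusted for age. For participants never dosed, take the last pre-treatment TUG as baseline, since SAP 5.1.1 does not clearly give them one. A TUG is scheduled at screening or Week 1 Day 1.
2. Amend SAP 4.2 with an explicit outcome rule for participants with no post-baseline TUG. Without one, the ban on imputation would still drop them from an FAS analysis. Imputation assuming missing at random is possible, but should not be presented as removing bias from informative loss. Also state how a stable Week 12 with a missing Week 24 is classified.
3. Name the FAS, without the post-baseline condition, as the set for the analysis that counts missing as worsened.
4. Add a two-directional or tipping-point version by arm, and report missing counts by arm.
5. Keep the Safety-population result as supportive.

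Align Protocol 9.3 and 9.4.2 with SAP 4.2, 5.1.1, 5.2, 5.5 and 5.5.1, and record the change in SAP 6.0.

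The cost is modest. Some outcomes are assigned by rule, especially for participants never dosed, and power when missing counts as worsened is about 78% to 79% at 10% missing in both arms. The protocol change is an amendment needing IRB/IEC approval under Protocol 10.1.1, which can be combined with the re-specification already planned.
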